### 2.2 State the hypotheses to be tested.

Aim 1: Hypotheses: The two intervention groups will demonstrate significant reductions in risky driving events (hard braking, sudden acceleration, speeding) and unsafe driving behaviors (speeding, no seatbelt use, distracted driving) per 1,000 miles driven when compared to the control group; The Driving-Feedback plus Parent Communication Training group will have fewer risky driving events and unsafe driving behaviors than the Driving Feedback Only group.

Aim 2: Hypothesis: The Driving-Feedback plus Parent Communication Training group will engage in more frequent and higher quality parent-teen communications on safe-driving topics than the other two groups.

Aim 3: Hypothesis: The two intervention groups will demonstrate significant reductions in recidivism (subsequent traffic violations) when compared to the Control group; The

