## PROTOCOL TITLE: Intervention to Improve Driving Practices Among High-Risk Teen Drivers

vehicle device installed in their car, but all feedback features will be disabled. If they are randomized into the Feedback Only Group, researchers will provide instructions on how teens can review their driving data. If in the Device Feedback plus Parent Communication Training Group, the NCH research team member will help schedule a video call with a specialist at the University of Iowa within 2 weeks of enrollment for parents to receive communication training on how to motivate their teen to adopt safe driving habits. This video call will be up to 45 minutes long and will take place 2 weeks after enrollment. The research team will also help schedule a booster session 2 months of the initial training session. Additionally, the member of our research team will show the parent how to access their teen's cumulative driving data. The teens of the Feedback Only Group will also receive a biweekly cumulative driving report. Teens and parents of the Device Feedback Plus Parent Communication Training Group will also receive a biweekly cumulative driving report as well as parental progress completing the online safe driving communication guide. Furthermore, we will obtain information about the teen's car year, make, and model for all participants regardless of group assignment. This initial meeting should take approximately 30 minutes.

The research team will reach out to participants at 3 months post-enrollment to have them fill out an online survey and terminate the active intervention for the intervention groups (Groups 2 & 3). At the end of 6 months, the NCH research team member will meet with participants in-person to end enrollment, and to collect the in-vehicle device. Additionally, they will administer a final survey to participants. After completion of this survey, participation in this study will be complete.

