## PROTOCOL TITLE: Intervention to Improve Driving Practices Among High-Risk Teen Drivers

details, ask questions, be screened for eligibility, and sign consent/assent documents either on-site in a private room or later at a time that is convenient to them. Only dyads with both parent and teen consent/assent will be enrolled. Enrolled participating dyads will then complete a baseline assessment before being randomly assigned into one of three study groups. The judge, who will not be engaged in study recruitment, will be blinded from the identity of dyads who choose to participate in the study and no other court staff will be involved with recruitment for this study. Refusal to participate in this study will have no penalty or loss of benefits to which teen drivers are otherwise entitled and will not affect the outcome of their court hearing in any way.

Virtual: We will have study flyers posted around the waiting room at the Juvenile Traffic Courts. We will share the testimonial video with the courts and other community/school events. Teens and parents who are interested will have the ability to scan the QR code on the flyer which will lead them to our eligibility screening form on REDCap. If the teens and parents are eligible, they will be contacted by our research team to schedule a meeting to virtually sign the consent/assent form and be enrolled in the study. If we contact the potential participant 3 or more times then we will assume they are not interested. We will send them a final email included in the script document. Only dyads with both teen and parent consent/assent will be enrolled. The judge, who will not be engaged in study recruitment, will be blinded from the identity of the dyads who choose to participate in the study. Refusal to participate in this study will have no penalty or loss of benefits to which teen drivers are otherwise entitled and will not affect the outcome of their court hearing in any way.

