## PROTOCOL TITLE: Intervention to Improve Driving Practices Among High-Risk Teen Drivers

6-month follow-up. To compare the differences among the 3 groups, one-way ANOVAs will be used. To model the effects of the intervention on the rates of risky driving events per 1,000 miles driven, a Quasi-Poisson analysis for over-dispersed count data will be conducted, where 2 dummy variables indicating Groups 2 and 3 will be created as covariates to determine risk ratios of risky driving events among the 3 groups, adjusting for the other potential covariates.

For the primary outcome of unsafe driving behaviors (speeding, distracted driving, no seatbelt use), to model the effects of the intervention on the proportion of unsafe behaviors per 1,000 miles driven, Quasi-Poisson analysis for over-dispersed count data will be implemented, where two dummy variables indicating Groups 2 and 3 will be created as covariates to determine the risk ratios of unsafe driving behavior among the 3 groups, adjusting for the potential covariates described above. In addition, a secondary analysis of correlation coefficients will be conducted to ascertain if and how the risky driving events and unsafe driving behaviors are correlated and whether the correlations are different between the study groups. The potential covariates will be adjusted.

For the secondary outcome of frequency and quality of parent-teen communication about driving safety, to model the effects of the intervention on differences in frequency and quality of parent-teen communication among the 3 groups, an Analysis of covariance (ANCOVA) will be used for each outcome, adjusting for the potential covariates. In addition, the following secondary analyses will be performed: 1) Correlation analysis will be conducted to examine if and how frequency and quality of parent-teen communication are correlated; 2) Longitudinal data analyses using mixed-effect models will be performed to further ascertain if the parent training enhances parent-teen communication over time with a focus on how these measures change over time in Group 3; 3) We will conduct further analysis on risky driving events and unsafe driving behaviors using the Quasi-Poisson analysis by including the measures of frequency and quality of parent-teen communication as three additional covariates to evaluate the effects of parent-teen communication, adjusting for group differences.

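### Two secondary analyses of Aim 2 lack the between-group contrast and the time order their questions need; the main three-group test is sound against common time trends

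*Combined protocol and SAP*

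**What the plan says.** Section 2.2 frames Aim 2 as a comparison: the feedback plus parent training group (Group 3) "will engage in more frequent and higher quality parent-teen communications on safe-driving topics than the other two groups". Section 17.1 answers this first with a comparison of the three groups, in which "an Analysis of covariance (ANCOVA) will be used for each outcome, adjusting for the potential covariates". The covariates are not listed in the available text, and the follow-up time point is not given.

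Section 17.1 then adds secondary analyses. Two matter here.

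- **Analysis 2** uses longitudinal mixed-effect models to "further ascertain if the parent training enhances parent-teen communication over time with a focus on how these measures change over time in Group 3". No group-by-time term and no contrast with Group 1 (control) or Group 2 (feedback only) is named. The text does not say whether those groups enter the model.
- **Analysis 3** refits the quasi-Poisson driving models, "including the measures of frequency and quality of parent-teen communication as three additional covariates to evaluate the effects of parent-teen communication, adjusting for group differences". It does not say which survey the communication measures come from. Section 17.1 calculates the risky-event rates at 6-month follow-up.

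The survey schedule appears to be the same in every group. Section 13.1 has in-person recruits "complete a baseline assessment before being randomly assigned into one of three study groups". Section 6.2 contacts participants "at 3 months post-enrollment to have them fill out an online survey and terminate the active intervention for the intervention groups", and at the 6-month visit says of the research team: "Additionally, they will administer a final survey to participants". Section 13.5 pays teen and parent for three surveys whatever their group.

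**The concern.** Analysis 2 asks a causal question, whether training improves communication, but points the reader at change within one group. Change in Group 3 mixes any training effect with whatever would have happened anyway. A shared drift is plausible. The frequency score in Section 6.4 uses past-month recall, and Section 6.1 puts the court appearance within two weeks of the citation, so for many court-recruited families the baseline month may contain the citation. Talk could then fade or grow in every group. A drift could create an apparent benefit or hide a real one.

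Analysis 3 speaks of effects of communication on driving without placing communication before driving. The reverse path is built into the design: Section 5.1 gives Group 3 parents access to their teen's driving data, and Section 6.2 sends them biweekly reports. A parent who sees poor driving may talk more. Adjusting for group does not remove this, because it operates within the group.

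At stake is the interpretation of two secondary results: whether training changes communication over time, and whether communication goes with safer driving.

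**Working it through.** **Inputs from the plan.** 74 evaluable dyads per group, 80 enrolled, over-dispersion factor 25, pilot mean 43 and SD 32.7 (all Section 17.1). The plan states no power or effect size for Aim 2, so there is no Aim 2 figure to reproduce. The over-dispersion used in step 3 does reproduce: 32.7² / 43 = 24.87, against the stated 24.9.

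**Assumptions.** Two-sided alpha 0.05, the drift sizes, and all correlations. None is given in the documents, so ranges are shown.

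**Step 1: reading analysis 2 from Group 3 alone.** Let the outcome have SD 1 at each survey and baseline-to-follow-up correlation r. The change score has SD √(2(1 − r)). With a drift d shared by all groups and no training effect, the one-group test of change has non-centrality d√74 / √(2(1 − r)). At r = 0.5 the change SD is 1 and √74 = 8.60, so d = 0.1, 0.2 and 0.3 give 0.86, 1.72 and 2.58. Rejection rates from the non-central t on 73 degrees of freedom:

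| Correlation r | d = 0.1 SD | d = 0.2 SD | d = 0.3 SD |
|---|---|---|---|
| 0.3 | 11.1% | 30.0% | 57.6% |
| 0.5 | 13.6% | 39.7% | 72.1% |
| 0.7 | 19.5% | 59.2% | 90.8% |

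With no drift the rate is 5%. In simulation at r = 0.5 (4,000 runs per drift), the contrast of change in Group 3 with change in Group 2 rejected in 5.2%, 5.3% and 5.4% of runs at the same three drifts. The shared trend cancels.

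**Step 2: baseline score in the ANCOVA.** Adjusting for the baseline value of the same score multiplies residual variance by 1 − r² and the standard error by √(1 − r²). At r = 0.5: √0.75 = 0.87, a 13% smaller standard error. At r = 0.7: √0.51 = 0.71, a 29% smaller one.

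**Step 3: analysis 3 under reverse causation.** Simulated trials had 3 × 74 = 222 teens, event counts with mean 43 and over-dispersion 25, no effect of communication on driving, and communication generated partly from driving. The quasi-Poisson model held two group indicators and one communication score (1,000 runs per row).

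| Assumed driving-to-communication correlation | Communication significant | Mean rate ratio per SD |
|---|---|---|
| 0 | 4.7% | 1.00 |
| 0.1 | 30% | 1.08 |
| 0.2 | 84% | 1.16 |
| 0.3 | 99% | 1.25 |

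The ratio exceeds 1: communication would look harmful, or a real benefit could be masked.

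**The case against.** The strongest reply is that the training effect on communication is already tested properly. The ANCOVA compares randomized groups, matches the hypothesis in Section 2.2, and is not biased by a trend common to all groups. Analysis 2 only supplements it. This stands. A reader might infer that the claim that training improves communication would rest on a non-randomized comparison; Section 17.1 does not support that.

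A focus on Group 3 also does not exclude Groups 1 and 2. A reader might infer a declared single-arm analysis, but the plan does not say so. What is missing is the contrast. Step 1 shows what follows if the stated focus is taken literally.

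A reader might also infer that reverse causation in analysis 3 could pass for a training effect. It could not: that model estimates the association of communication with driving, with group terms retained. Those group terms are, however, conditional on a post-randomization variable and should not be read as intervention effects.

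The drift is not documented. For court recruits the citation and hearing precede baseline, which weakens the case for an upward drift prompted by the hearing but leaves room for a fade after it. Lastly, leaving out the baseline score costs precision and does not bias a randomized comparison. The general reference to potential covariates does not rule it out. The survey forms are attachments (Section 6.3.2) and the baseline content is not itemized, so its availability is an inference.

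**Conclusion.** The point holds for two secondary analyses. Analysis 2 needs a named between-group contrast. Without one, a shared drift of 0.1 to 0.3 SD would be credited to training in about 14% to 72% of trials at correlation 0.5, against about 5% when groups are compared. Analysis 3 needs a time order and an exploratory label. At assumed driving-to-communication correlations of 0.1 to 0.3, a null communication covariate is significant in 30% to 99% of trials. The drifts and correlations are illustrations, not estimates for this trial.

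Naming the baseline score is a separate gain in precision for the main ANCOVA: a 13% to 29% smaller standard error at an assumed correlation of 0.5 to 0.7. The validity of the main Aim 2 test, the primary driving comparisons and the sample size do not depend on this point.

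**What to change.** 1. **Analysis 2.** Fit the mixed model to all three groups at baseline, 3 and 6 months. Make the group-by-time contrasts the test: Group 3 minus Group 2 and Group 3 minus Group 1, at 3 and at 6 months. Change within Group 3 can be reported as description.
2. **ANCOVA.** Name the baseline score of the same measure as a covariate, once the sponsor confirms that the baseline survey contains it.
3. **Analysis 3.** State which survey supplies the communication scores and label the result an exploratory association. Add a time-ordered version in which month-3 communication predicts the event rate in months 4 to 6, adjusting for group and the months 1 to 3 rate.

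Items 1 and 2 are changes of wording that use surveys already planned and paid for in every group. Item 3 needs no new collection, since the device stays in the car for six months (Section 6.2), but it has a price. The time-ordered version uses about half the driving exposure; if information scales with exposure (an assumption), the standard error rises by up to √2 = 1.41, or 41%. It covers only the period after active intervention ends at 3 months. Adjusting for months 1 to 3 conditions on driving after training has begun and may remove part of an early effect. The result remains observational, so it should accompany the association in analysis 3 and not be presented as causal.

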### **17.2 Describe the steps that will be taken to secure the data (e.g., training, authorization of access, password protection, encryption, physical controls, certificates of confidentiality, and separation of identifiers and data) during storage, use, and transmission.**

A unique participant ID will be created for each subject. The list linking the assigned ID to the individual subject will be maintained separately from the other research data. All data files used for analysis will only have the ID and will not contain any other personal information. Data will be stored on secure, password protected computers.

### **17.3 Describe any procedures that will be used for quality control of collected data.**

N/A

### **17.4 Describe how data or specimens will be handled study-wide:**

#### **17.4.1 What information will be included in that data or associated with the specimens?**

Participant data will have unique participant IDs that are stored on a secure password protected computer.

#### **17.4.2 Where and how data or specimens will be stored?**

Until completion of the study.

**17.4.3 How long the data or specimens will be stored?**

Until completion of the study.

**17.4.4 Who will have access to the data or specimens?**

Research team members.

**17.4.5 Who is responsible for receipt or transmission of the data or specimens?**

Research team members.

**17.4.6 How data or specimens will be transported?**

By research team members.

**18.0 Provisions to Protect the Privacy Interests of Subjects**

**18.1 Describe the steps that will be taken to protect subjects' privacy interests. "Privacy interest" refers to a person's desire to place limits on whom they interact or whom they provide personal information.**

A unique participant ID will be created for each subject. The list linking the assigned ID to the individual subject will be maintained separately from the other research data on password protected computers. All data files used for analysis will only have the ID and will not contain any other personal information.

**18.2 Describe what steps you will take to make the subjects feel at ease with the research situation in terms of the questions being asked and the procedures being performed. "At ease" does not refer to physical discomfort, but the sense of intrusiveness a subject might experience in response to questions, examinations, and procedures.**

All participants will be given a phone number that connects them to a research team member. Participants can call and ask research related questions at any time (24/7).

**18.3 Indicate how the research team is permitted to access any sources of information about the subjects.**

Our research team will not access any source of personal information about the subjects.

**19.0 Economic Burden to Subjects**

**19.1 Describe any costs that subjects may be responsible for because of participation in the research.**

All costs related to the research parts of this study will be covered by the research team. However, the parts of the study that would be done for routine clinical care will be billed to an insurance company or third party payer. Further, if a participant were to be involved in a crash while participating in this study, participants are responsible for any costs associated with damages. Participants may have to pay any costs that the insurance company or third party payer does not pay. There may be additional costs related to travel during this study. We will not provide money to help with these costs. A parking voucher will be provided if participants come to NCH for a study visit. This reimbursement may be taxable. The study team will discuss this with participants.

**20.0 Consent Process**

**20.1 Indicate whether you will be obtaining consent, and if so describe:**

**20.1.1 Where will the consent process take place**

In-person: Consent will take place at various Ohio Juvenile Traffic Courts in a private room near the courtroom or at location convenient for the participants (i.e., participant home, school, library).

Virtual: Consent will take place over video conference with the researcher, teen, and parent present. The consent will be signed through REDCap.

**20.1.2 Any waiting period available between informing the prospective subject and obtaining the consent.**

If participants want time to consider participation, research team members will give them time for consideration.

**20.1.3 Any process to ensure ongoing consent.**

N/A

**20.1.4 Whether you will be following “SOP: Informed Consent Process for Research (HRP-090).” (Yes)**

*Subjects who are not yet adults (infants, children, teenagers)*

**20.1.5 Describe the criteria that will be used to determine whether a prospective subject has not attained the legal age for consent to treatments or procedures involved in the research under the applicable law of the jurisdiction in which the research will be conducted. (E.g., individuals under the age of 18 years.)**

Participants will be asked their age, and their age will be confirmed by a legal guardian.

**20.1.6 Describe whether parental permission will be obtained from:**

One parent even if the other parent is alive, known, competent, reasonably available, and shares legal responsibility for the care and custody of the child.

**20.2 Indicate whether assent will be obtained from all, some, or none of the children. If assent will be obtained from some children, indicate which children will be required to assent. When assent of children is obtained describe whether and how it will be documented.**

Written assent of the child will be obtained and documented at the same time written consent from a parent/legal guardian is obtained.

**21.0 Process to Document Consent in Writing**

**21.1 Describe whether you will be following “SOP: Written Documentation of Consent (HRP-091).” If not, describe whether and how consent of the subject will be documented in writing.**  
Yes, we will collect written documentation of consent.

**22.0 Setting**

**22.1 Describe the sites or locations where your research team will conduct the research.**

**22.1.1 Identify where your research team will identify and recruit potential subjects.**

In-person: Identification and recruitment of individuals will occur at various Juvenile Traffic Courts in Ohio such as the Franklin County Juvenile Traffic Court and at different venues such as Car teens.

Virtual: Potential participants will have the ability to scan a QR code at the various Juvenile Traffic Courts and different local Franklin County Juvenile Traffic Court in Columbus, Ohio and through multiple online avenues including social media, research databases (e.g., Studysearch, ResearchMatch), and other relevant listservs (e.g. Peachjar).

**22.1.2 Identify where research procedures will be performed.**

Research procedures will occur at the courthouse and at the participant’s home (or a location that is convenient to them based on their personal preference).

**22.1.3 Describe the composition and involvement of any community advisory board.**

N/A

**23.0 Resources Available**

**23.1 Describe the resources available to conduct the research: For example, as appropriate:**

**23.1.1 Justify the feasibility of recruiting the required number of suitable subjects within the agreed recruitment period. For example, how many potential subjects do you have access to? What percentage of those potential subjects do you need to recruit?**

With our previous pilot study, our research team demonstrated success recruiting from the courthouse. Specifically, for our pilot study we were able to enroll 10 parent-teen dyads within one week. Based on existing traffic citation and court disposition data, the number of teens 16- or 17-years who committed a traffic violation(s) was 2,843 in 2016 and 2,847 in 2017, 13% of whom had a previous offense. These numbers provide an ample base

